## **9. ETHICS**

The study complies with the Declaration of Helsinki. Ethical approval was obtained from the Uşak University Non-Interventional Clinical Research Ethics Committee (Decision Number: 352-352-10). Written informed consent will be obtained from all participants.

## **10. STUDY TIMELINE**

- Recruitment: May 2024 - October 2024
- Intervention: October 2024
- Data Collection: November 2024
- Analysis and Reporting: December 2024 - March 2025

# STATISTICAL ANALYSIS PLAN

## STATISTICAL ANALYSIS PLAN (SAP)

- Intention-to-Treat (ITT): Includes all randomized participants who completed at least one session.
- Per-Protocol (PP): Includes only participants who completed all four sessions.

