**Exclusion Criteria:**

- Age below 40 or above 65 years.
- On insulin therapy for more than 3 months.
- Mental or psychological comorbidities.
- Declining to participate or incomplete participation in all four sessions.

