## **7. DATA COLLECTION**

Data will be collected at two time points:

Pre-test: Before the first intervention session.

Post-test: After the final session.

Instruments:

- Beck Anxiety Scale (BAS)
- Patient Compliance Scale for Type 2 Diabetes Mellitus Treatment

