## DATA MANAGEMENT

- Data will be entered and stored securely with anonymized participant IDs.
- Data quality checks will be performed to identify inconsistencies or missing data.
- Missing data will be handled using listwise deletion for final analyses.

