### Primary Outcome Analyses

- Within-group analysis: Paired t-test comparing pre-test and post-test scores for anxiety and adherence.
- Between-group analysis: Independent t-test comparing post-test mean differences between intervention and control groups.

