## **HANDLING DROPOUTS**

- Participants who miss one or more intervention sessions will be excluded from the Per-Protocol analysis but included in the Intention-to-Treat analysis if they completed pre-test measurements.

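### The protocol excludes patients who miss sessions, the SAP keeps them in its intention-to-treat set, and neither says which analysis set is primary

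*Combined protocol and SAP*

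**What the plan says.** Five places bear on who is analysed.

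- **Protocol section 3, Exclusion Criteria:** "Declining to participate or incomplete participation in all four sessions".
- **SAP, opening section:** "Intention-to-Treat (ITT): Includes all randomized participants who completed at least one session", followed by "Per-Protocol (PP): Includes only participants who completed all four sessions".
- **SAP, Handling Dropouts:** "Participants who miss one or more intervention sessions will be excluded from the Per-Protocol analysis but included in the Intention-to-Treat analysis", on condition that the pre-test was done. Protocol section 7 places that measurement early: "Pre-test: Before the first intervention session".
- **SAP, Primary Outcome Analyses:** "Between-group analysis: Independent t-test comparing post-test mean differences between intervention and control groups". No analysis set is attached to this test. Protocol section 8 also lists tests without a set.
- **SAP, Data Management:** "Missing data will be handled using listwise deletion for final analyses".

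Neither document gives an order of precedence between the protocol's exclusion list and the SAP's set definitions. Neither ranks ITT against PP.

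**The concern.** An eligibility criterion should be checkable before randomisation. Attendance at weekly sessions is not, so the section 3 item can act only by removing patients after allocation. The SAP says that such patients stay in ITT. The same patient is therefore both excluded and included.

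The arms differ in teaching format, game or lecture, so attendance may depend on the arm. It may also be related to anxiety and treatment adherence, the two primary outcomes. If both hold and the arms lose patients unequally, a comparison restricted to attenders is no longer protected by randomisation.

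Separately, with two sets and none named primary, the set could be chosen once the results are known.

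A lesser point is that the set called ITT is not all randomised participants, since it requires at least one session.

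**Working it through.** **1. The rules side by side, for a randomised patient with a pre-test**

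| Sessions attended | Protocol section 3 | SAP ITT definition | SAP dropout rule | PP |
|---|---|---|---|---|
| 4 | in | in | not addressed | in |
| 1 to 3 | excluded | in | in ITT | out |
| 0 | excluded | out | in ITT | out |

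The main conflict is the middle row. If section 3 is enforced after randomisation, only the top row remains and ITT equals PP. The bottom row is a smaller conflict within the SAP itself.

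**2. The plan's own figure.** A two-sample t-test with effect size 0.768, two-sided 5% and 85% power (noncentral t) needs 32 per group (power 85.6%), which matches protocol section 4. With 36 per group, power is 89.5%. The sample size is not in dispute.

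**3. Bias from selecting on attendance.** The removal fractions and correlations are assumptions. Suppose arms 1 and 2 lose their lowest fractions q1 and q2 on an attendance propensity that has correlation r with the outcome. Then

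bias (SD) = r × [φ(z_q1)/(1−q1) − φ(z_q2)/(1−q2)].

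The term φ(z_q)/(1−q) is 0.109 at 5%, 0.195 at 10% and 0.350 at 20%. Type I error is from the noncentral t.

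| Removed | Analysed | r | Bias (SD) | Type I error |
|---|---|---|---|---|
| 10% v 5% | 32 v 34 | 0.3 | 0.3 × 0.086 = 0.026 | 5.12% |
| 10% v 5% | 32 v 34 | 0.5 | 0.5 × 0.086 = 0.043 | 5.34% |
| 20% v 5% | 29 v 34 | 0.1 | 0.1 × 0.241 = 0.024 | 5.10% |
| 20% v 5% | 29 v 34 | 0.3 | 0.3 × 0.241 = 0.072 | 5.92% |
| 20% v 5% | 29 v 34 | 0.5 | 0.5 × 0.241 = 0.121 | 7.57% |

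With q1 = q2 and the same r in both arms, the bracket is zero.

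**4. The at-least-one-session rule alone.** Losing 1 or 2 of 36 in one arm and none in the other, at r from 0.3 to 0.5, gives 0.02 to 0.06 SD and 5.1% to 5.7%.

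**5. Choosing the set afterwards.** Trials with 36 per arm and no effect were simulated (at least 100,000 per case, Monte Carlo error below 0.1 point). A trial counted if either set was significant.

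- Attendance unrelated to outcome, with PP dropping 2, 4 or 7 per arm: about 6.1%, 6.5% and 7.1%.
- Attendance related to outcome, with 7 v 2 of 36 dropped: about 8% at r = 0.3 and just under 10% at r = 0.5.

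**The case against.** The best defence is that section 3 is loose drafting. It joins refusal and non-attendance in one enrolment list, and the SAP has a specific rule for patients who miss sessions. A specific analysis rule can reasonably be read as governing a general eligibility line. That reading is workable, but no text adopts it, and it leaves the primary set unnamed.

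It is also fair that the ITT definition states its condition openly, so that part of the fault is largely the label. Its effect in step 4 is small.

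A reader might infer three stronger things that the documents do not support.

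- *That incomplete attenders will be dropped and ITT will collapse into PP.* This follows only if section 3 is enforced after randomisation, and nothing says that it will be.
- *That the comparison is biased by a known amount.* No attendance rate or attendance-outcome correlation is given, and equal loss of the same kind in both arms gives no selection bias.
- *That 6% to 7% is a ceiling on the error from choosing the set afterwards.* It applies only when attendance is unrelated to outcome. The related, unequal case in step 5 exceeds it.

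**Conclusion.** Wrong as written, on two grounds that need no assumption: the protocol's exclusion contradicts the SAP's treatment of patients who miss sessions, and no set is named primary. The mislabelled ITT set, and its clash with the dropout rule over a patient with a pre-test and no session, is a lesser fault that would not carry the point alone.

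The sizes rest wholly on assumed attendance. They run from negligible (5.1% type I error) to moderate (7.6% from selection, up to about 10% if the set is also chosen by result). If every patient attends all sessions and gives complete data, the sets coincide and nothing is lost. The case for change rests on the contradiction and the open choice, not on these figures.

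**What to change.** 1. In protocol section 3, delete the attendance item as a ground for removal from analysis.
2. In the SAP's set definitions and dropout rule, use one definition: ITT is all randomised participants, analysed as assigned, whatever number of sessions they attended.
3. Under Primary Outcome Analyses, name ITT as primary and PP as sensitivity.
4. Analyse every post-test obtained. State that under listwise deletion the analysed set is those ITT patients with outcome data.
5. In the CONSORT diagram, report by arm and reason those excluded or without a post-test. Include any whose post-test was not collected because section 3 was enforced; rewording cannot recover those data.
6. The timeline puts data collection in November 2024 and analysis in December 2024. If the data had already been analysed, date the choice and disclose it as made after data collection.

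**Cost.** Wording, plus some dilution. Suppose k game-arm patients are incomplete, k0 of them attended nothing, none of the k gains anything, 0.768 is a full-attendance effect (protocol section 4 does not say so), and all 36 per arm have a post-test. The effect is 0.768 × (36−k)/(36−k0) with 36−k0 v 36 under the SAP's present ITT, and 0.768 × (36−k)/36 with 36 v 36 under the fix.

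| k, k0 | Present ITT | Fix | Difference |
|---|---|---|---|
| 1, 1 | 89.1% | 87.8% | 1.3 points |
| 4, 1 | 83.1% | 81.5% | 1.6 points |
| 4, 2 | 84.6% | 81.5% | 3.1 points |
| 7, 2 | 77.0% | 73.5% | 3.5 points |

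If partial attenders gain half the benefit, the 4, 1 case becomes 86.3% v 84.9%: power rises in both sets and the difference stays small.

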## DATA MANAGEMENT

- Data will be entered and stored securely with anonymized participant IDs.
- Data quality checks will be performed to identify inconsistencies or missing data.
- Missing data will be handled using listwise deletion for final analyses.

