## **SIGNIFICANCE LEVEL**

- All statistical tests will be two-tailed, with a significance threshold of  $p < 0.05$ .

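### Listwise deletion removes ITT participants who have no post-test, so the result labelled ITT is an outcome-completer result, open to bias when missingness is related to outcome and differs between arms

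*Combined protocol and SAP*

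**What the plan says.** The SAP's missing-data rule, under Data Management, is one sentence: "Missing data will be handled using listwise deletion for final analyses". It makes no exception for any analysis set.

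Under Handling Dropouts, a participant who misses sessions leaves the per-protocol set but is "included in the Intention-to-Treat analysis if they completed pre-test measurements". No post-test is required. The analysis-set list that opens the SAP defines ITT differently: "Includes all randomized participants who completed at least one session". Per-protocol is narrower: "Includes only participants who completed all four sessions".

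Protocol section 7 states "Data will be collected at two time points", one before the first session and one afterwards. The SAP's between-group primary analysis is "Independent t-test comparing post-test mean differences between intervention and control groups", and the within-group analysis is a paired t-test of pre-test against post-test.

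The protocol's exclusion criteria (section 3) also list "Declining to participate or incomplete participation in all four sessions", and attendance is known only after randomisation.

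Neither document plans imputation, a likelihood-based model or a missing-data sensitivity analysis. Neither says that the post-test is to be sought from people who stop attending.

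**The concern.** A participant with a pre-test and no post-test is included by one SAP rule and removed by another. With no interim score, such a person contributes nothing to any primary test. The analysis called ITT then covers only those who supplied a post-test, and the protection of randomisation holds only if that selection is unrelated to outcome or acts alike in both arms.

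That cannot be taken for granted here. The outcomes are anxiety and treatment adherence, and both could plausibly influence who finishes a four-week course and returns for a questionnaire. A board game and a lecture course may also lose different kinds of people. Readers would take the ITT label as assurance against this selection, which the analysis would not give.

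**Working it through.** **1. The rules side by side**

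| Participant (all with a pre-test) | Handling Dropouts | After listwise deletion |
|---|---|---|
| Misses a session, gives a post-test | in ITT | analysed |
| Misses a session, no post-test | in ITT | deleted |
| Attends all four, no post-test | not covered by this rule; in ITT by the opening list | deleted |
| Randomised, attends none | in ITT here, out of ITT by the opening list | depends on which definition is used |

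The rules collide in the second and third rows. The last row shows that the two ITT definitions also differ.

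**2. The plan's own sample size**

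Inputs from protocol section 4: effect size 0.768, power 85%, 95% confidence; the SAP specifies two-tailed tests at 0.05.

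- Normal approximation: n = 2(1.960 + 1.036)² / 0.768² = 30.4, so 31 per arm.
- Exact noncentral t: 32 per arm, power 85.6%. The stated minimum of 32 reproduces.
- The planned 36 per arm gives 89.5%. Moving from 36 back to 32 is a loss of 1 − 32/36 = 11.1%. The protocol does not call this a dropout allowance.
- With 29 or 26 analysed per arm, power is 82.0% or 77.5%.

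Up to about 11% loss per arm the issue is bias, not power.

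**3. Bias when loss depends on pre-test anxiety**

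Assumptions, none from the documents: no true effect, 36 per arm, pre-post correlation 0.6, log-odds of loss rising by 1.0 to 1.5 per SD of pre-test anxiety. Results are for the unadjusted t-test on post-test scores.

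| Loss, arm A v arm B | Apparent advantage of arm A | Type I error |
|---|---|---|
| 15% v 8% | 0.03 to 0.05 SD | about 5.4% |
| 20% v 5% | 0.07 to 0.10 SD | about 6% |
| 30% v 5% | 0.12 to 0.16 SD | about 7 to 9% |

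Repeat simulations differ by a few tenths of a percentage point in type I error. Four further results mark the limits:

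- Loss unrelated to anxiety, even at 30% v 5%: bias about zero.
- Equal 20% loss with the same mechanism in both arms: zero.
- Equal 20% loss with opposite mechanisms (correlation 0.5, log-odds 1.5): about 0.23 SD.
- Baseline-adjusted analysis of the same retained participants: 0.006 SD or less in the tabulated 20% v 5% and 30% v 5% scenarios.

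**4. Bias when non-returners do worse for reasons the pre-test does not capture**

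If non-returners' post-tests are g SD worse than those of returners, the mean among returners exceeds the arm mean by (loss rate × g). Hence bias = (loss in A × gap in A) − (loss in B × gap in B). With the same gap in both arms:

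- 20% v 5%: (0.20 − 0.05) × 0.25 = 0.04 SD, and (0.20 − 0.05) × 1.0 = 0.15 SD. With 29 v 34 analysed, type I error is 5.2% to 9.0%.
- 30% v 10%: 0.20 × 0.25 = 0.05 SD, and 0.20 × 1.0 = 0.20 SD. With 25 v 32 analysed, type I error is 5.4% to 11.4%.

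**5. Direction**

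Reversing the rates reverses the sign: 5% game v 20% control gives 0.07 to 0.10 SD against the game. The sign also turns on how the SAP's between-group test is read. If it means change scores, the step 3 assumptions give 0.05 to 0.07 SD (20% v 5%) and 0.08 to 0.11 SD (30% v 5%) against the arm that loses more.

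**The case against.** The strongest reply is that the two rules address different things, missed sessions and missing data, and can both operate. Someone who skips a session and returns for the post-test is kept by both, and section 5 of the protocol does not limit the post-test to attenders. That is correct. A reader might infer that every dropout is lost, or that ITT collapses into the per-protocol set; the documents support neither. What stands is the narrower conflict over participants with no post-test, which nothing in the documents resolves.

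A second reply is that the size and direction are not established. This also stands. A reader might infer that unequal dropout by itself biases the comparison, or that the bias flatters the game. The first fails because loss unrelated to outcome gives no bias. The second has no support: the documents do not say which arm will lose more, and the protocol's background expects games to improve motivation.

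A third reply is that, where loss is driven by the pre-test, the unadjusted t-test is at fault as much as the deletion, since adjustment removes the bias from the same retained data. That is right, and it shapes the fix. It does not cover step 4, where the pre-test does not explain the loss.

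Finally, a reader might infer that deletion spreads across outcomes, so that a blank adherence form also removes the anxiety score. With 5% independently missing on each scale that would cost 1 − 0.95² = 9.75%, or 7 of 72. The SAP does not say that the two scales share one listwise run, so this is only something for the wording to rule out.

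**Conclusion.** The concern holds in a limited form. That the plan would label an outcome-completer analysis as ITT is certain from the text, provided any randomised participant lacks a post-test. Whether the result is biased is conditional: missingness must be related to outcome, and its rate or mechanism must differ between arms.

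Under the stated assumptions the bias runs from about 0.03 SD with mild imbalance to 0.16 SD with severe baseline-driven imbalance, and reaches 0.20 SD if non-returners at 30% v 10% are a full SD worse. Against the planned 0.768 these are roughly 4%, 21% and 26%. Type I error ranges from little above 5% to about 11%. The opposite-mechanism case (0.23 SD) shows that equal dropout rates would not by themselves be reassuring. Confidence is high on the conflict and low on the size and sign of any bias. The plan should be changed, but the conflict alone does not invalidate the trial.

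**What to change.** **Protocol sections 5 and 7.** State that the post-test is sought from every randomised participant whatever their attendance, unless consent is withdrawn. Reconcile the two post-test times: section 5 puts it one month after the intervention ends, section 7 after the last session.

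**Protocol section 3, the SAP's analysis-set list and Handling Dropouts.** Use one ITT definition: all randomised, analysed as assigned. State that incomplete attendance after randomisation affects only the per-protocol set.

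**SAP, Data Management and Primary Outcome Analyses.** For the ITT analysis, replace listwise deletion with:

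- ANCOVA on the pre-test score, each outcome on its own available data, which also settles the post-test versus change-score ambiguity;
- multiple imputation of missing post-tests from the pre-test scores and baseline covariates;
- a sensitivity analysis that shifts the imputed scores in each arm, in either direction, until the conclusion changes. This is needed because adjustment and imputation from baseline data cannot correct loss that those data do not explain.

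Report missing post-tests by arm and reason, alongside the CONSORT diagram already planned.

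**Cost.** SAP wording, some extra analysis, follow-up of non-attenders with two questionnaires already in use, and possibly a slightly wider interval. If collection has finished (scheduled for November 2024), the analysis changes can still be made from the pre-test data.

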## STATISTICAL SOFTWARE

All analyses will be conducted using \*\*SPSS version 25.0\*\*.

## DESCRIPTIVE ANALYSIS

- Continuous variables: Mean  $\pm$  Standard Deviation (SD), Minimum, Maximum.
- Categorical variables: Frequencies and Percentages.

## STATISTICAL METHODS

### Baseline Comparisons

- Independent samples t-test for continuous baseline characteristics (e.g., age, baseline anxiety).
- Chi-square test for categorical variables (e.g., gender, marital status).

### Primary Outcome Analyses

- Within-group analysis: Paired t-test comparing pre-test and post-test scores for anxiety and adherence.
- Between-group analysis: Independent t-test comparing post-test mean differences between intervention and control groups.

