**4. SAMPLE SIZE**

The sample size was calculated using G\*Power 3.1.9.2 at a 95% confidence level, effect size 0.768, and power of 85%.

- Minimum required per group: 32 participants
- Total sample size: 72 participants (36 in each group)

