## **8. STATISTICAL ANALYSIS**

- Statistical analyses will be conducted using SPSS version 25.0.
- Descriptive statistics: mean, standard deviation, frequency, and percentage.
- Independent t-tests will be used for between-group comparisons.
- Paired t-tests for within-group comparisons.
- Pearson correlation for relationships between anxiety and adherence.
- Significance level set at  $p<0.05$ .
- Cronbach's alpha will be used to assess the reliability of scales.

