## **NORMALITY AND ASSUMPTIONS**

- Normality will be assessed using Kurtosis and Skewness statistics.
- Homogeneity of variances will be checked using Levene's test.
- If assumptions are violated, non-parametric equivalents (Mann-Whitney U test, Wilcoxon Signed-Rank test) will be applied.

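### The primary between-group t-test leaves the collected pre-test unused and can be read two ways; a pre-specified ANCOVA would settle the reading and gain precision at almost no cost

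*Combined protocol and SAP*

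**What the plan says.** Protocol section 8 says only that "Independent t-tests will be used for between-group comparisons". The SAP, under Primary Outcome Analyses, is more specific: "Between-group analysis: Independent t-test comparing post-test mean differences between intervention and control groups". The bullet just before it reads "Within-group analysis: Paired t-test comparing pre-test and post-test scores for anxiety and adherence".

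Protocol section 7 schedules a baseline measurement on both primary scales: "Pre-test: Before the first intervention session". The plan uses it in the within-arm paired tests, and the SAP's Baseline Comparisons section tests baseline anxiety between arms. Neither document names ANCOVA, a regression model or any adjustment for baseline in the between-group comparison.

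The sample size (protocol section 4) was calculated "at a 95% confidence level, effect size 0.768, and power of 85" per cent. This gives a minimum of 32 per group, with 36 per group planned. Under Normality and Assumptions the SAP adds: "If assumptions are violated, non-parametric equivalents (Mann-Whitney U test, Wilcoxon Signed-Rank test) will be applied". It names skewness, kurtosis and Levene's test as the checks but gives no cut-off for skewness or kurtosis.

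**The concern.** There are two linked issues and one secondary one.

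- **Unused information.** A pre-test on the same scale usually predicts the post-test. Leaving it out of the between-group model forgoes precision that needs no extra data or recruitment.
- **Two readings.** The phrase about post-test mean differences most naturally means post-test scores, because the neighbouring bullet names both pre-test and post-test when both are meant. It can also mean the difference between arms in mean change, and nothing else in the documents rules that out. These are different analyses with different power, and the choice could be made after the data are seen, for both primary outcomes.
- **Secondary: the switch to a rank test.** With no stated skewness or kurtosis cut-off, the data decide whether the primary result is a mean difference or a rank comparison. Mann-Whitney is not a test of equal means when the spreads differ.

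**Working it through.** **Inputs from the documents.** Standardised effect d = 0.768, power 85%, minimum 32 and planned 36 per arm (protocol section 4); two-sided 0.05 (SAP, Significance Level).

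**Assumed, because the documents do not give them.** The pre/post correlation r, equal pre and post SDs, and whether 0.768 is in post-score or change-score SD units.

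**1. The plan's own figure.** Two-sample t-test, noncentrality = 0.768 × √(n/2), df = 2n − 2.
- n = 31: noncentrality 3.024, power 84.5%
- n = 32: 0.768 × 4 = 3.072, power 85.6%
- n = 36: 0.768 × √18 = 3.258, power 89.5%

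The stated 32 per group is reproduced. In simulations with normal data at 36 per arm, type I error was 4.8 to 5.1% for the post-test t-test, the change-score t-test and ANCOVA.

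**2. Three analyses at 36 per arm, 0.768 in post-score SD units.** Noncentrality = 0.768 × √(n/(2v)), where:
- post-test t-test: v = 1
- change-score t-test: v = 2(1 − r)
- ANCOVA: v = (1 − r²)(1 + t²/(2n − 2)), averaged over the chance pre-test imbalance t, which follows a t distribution on 2n − 2 df; test on 2n − 3 df

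Example, r = 0.3: for change, v = 1.4 and 3.258/√1.4 = 2.754, power 77.5%. For ANCOVA, 1 − r² = 0.91 and 3.258/√0.91 = 3.416 before the imbalance term, power 91.7% after it.

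| r | Post-test | Change | ANCOVA | ANCOVA n per arm for 85% |
|---|---|---|---|---|
| 0 | 89.5% | 62.3% | 89.1% | 32 |
| 0.3 | 89.5% | 77.5% | 91.7% | 30 |
| 0.5 | 89.5% | 89.5% | 95.7% | 25 |
| 0.7 | 89.5% | 98.6% | 99.4% | 18 |

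**3. The same, 0.768 in change-score SD units.** The mean difference is then 0.768 × √(2(1 − r)) score SDs.

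| r | Post-test | Change | ANCOVA |
|---|---|---|---|
| 0 | 99.5% | 89.5% | 99.5% |
| 0.3 | 96.7% | 89.5% | 97.7% |
| 0.5 | 89.5% | 89.5% | 95.7% |
| 0.7 | 70.2% | 89.5% | 93.3% |

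At r = 0.3 the two readings of the t-test differ by 12 or 7 points, depending on the units; at r = 0.5 they do not differ.

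**4. Unequal SDs.** With k = post SD / pre SD, the change score has v = 1 + 1/k² − 2r/k. At r = 0.3 (post-score units), k = 0.7 gives v = 2.184 and 58.5% power; k = 1.3 gives v = 1.130 and 85.6%. ANCOVA stays at 91.7%.

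**5. Confidence interval.** The half-width is t(0.975) × √(2v/n), with v = 1 − r² and a factor √(1 + 1/(2n − 4)) for ANCOVA. In SD units it is 0.470 for the post-test t-test and, for ANCOVA, 0.452 at r = 0.3 and 0.410 at r = 0.5.

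**6. Break-even.** At 36 per arm, ANCOVA and the post-test t-test have equal power at r = 0.12.

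**7. The rank-test switch, by simulation.** Assumed: gamma-shaped scores, 36 per arm, equal means, and Mann-Whitney used if Levene p < 0.05 or if absolute skewness or excess kurtosis in either arm exceeds 1.5 or 2. Rejection rates:

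| SD ratio | Shape 4 | Shape 2 | Shape 1 |
|---|---|---|---|
| 1 | about 5% | about 5% | about 5% |
| 1.5 | about 7% | about 9% | about 17% |
| 2 | about 10% | about 16% | about 29% |

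In the unequal-spread settings the plain t-test rejects about 5 to 6%, and ANCOVA (r = 0.3 or 0.5) 4.8 to 6.2%.

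**The case against.** The strongest reply is that this is an efficiency preference. The planned test is valid, the sample size is right, and on the natural reading the trial has 89.5% power against a target of 85%. At r = 0.3 ANCOVA adds only 2.2 points. The larger gains need r of 0.5 or more, and the documents give no r. The ambiguity could be removed by one clarifying phrase, without ANCOVA. All of this stands, and it limits how strongly the point should be put. It does not remove the case: the same edit that settles the wording can also use the baseline, and the worst loss is about half a point.

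Adjustment could also lose participants. The SAP's first definition of the intention-to-treat set, "Includes all randomized participants who completed at least one session", does not require a pre-test, and "Missing data will be handled using listwise deletion for final analyses". But Handling Dropouts makes a completed pre-test a condition for including those who miss sessions, and the pre-test precedes the first session, so such losses may be few.

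On the rank test, the skewness, SD ratios and cut-offs are all assumed, and inflation is much smaller at ratio 1.5 than at 2. The protection comes from not switching tests rather than from ANCOVA. That is correct, which is why the point is secondary and the ANCOVA recommendation does not depend on it.

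**Conclusion.** The point holds as a low-cost improvement that should be made. The primary comparison does not use a baseline collected on both primary scales, and its wording leaves the outcome variable open. With 0.768 in post-score SD units and r between 0.3 and 0.5, ANCOVA adds 2.2 to 6.2 power points over the post-test t-test at 36 per arm and needs 30 to 25 per arm rather than 32 for 85% power. That widens the margin for dropout. The size of the gain rests on an assumed r; below about 0.12 there is a slight loss.

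No bias and no sample-size error is shown. Calling the t-test valid refers to the test on complete randomised data. It does not extend to exclusions for incomplete sessions, listwise deletion or the two differing intention-to-treat definitions, none of which ANCOVA repairs.

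**What to change.** In protocol section 8 and the SAP's Primary Outcome Analyses, for the two primary outcomes, write: *Between-group analysis: ANCOVA of the post-test score on arm, with the pre-test score of the same scale as covariate, reporting the adjusted mean difference with 95% CI.*

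Under Normality and Assumptions, write: *The adjusted mean difference remains the primary result whatever the assumption checks show; the Mann-Whitney U test is reported as a sensitivity analysis.*

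The change counts as pre-specified only if it is made before outcome data are seen. The plan's own timeline puts data collection in November 2024 and statistical analysis in December 2024; a later change should be labelled post hoc.

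Costs:
- Wording only, with no new data. One degree of freedom, worth about 0.5 power points at r = 0.
- Anyone without a pre-test drops out of the model. ANCOVA still matches the post-test t-test at 36 per arm with 34 per arm at r = 0.3 or 28 at r = 0.5, so the gain survives up to 2 or 8 missing pre-tests per arm.
- Demoting the rank test gives up some power if scores are skewed and the effect is a pure shift. For a 0.768 SD shift with gamma shapes 4, 2 and 1, Mann-Whitney has 92.3, 95.7 and 98.3%. ANCOVA has about 91 to 92% at r = 0.3 and 95 to 96% at r = 0.5.

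One matter needs separate reconciliation before the model is final: the Follow-up paragraph in section 5 puts the post-test one month after the intervention ends, whereas section 7 puts it after the last session.
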